6.1.2 Additional study treatments

No other study treatment beyond investigational drugs (sabatolimab and azacitidine) is included in this trial.

6.1.3 Treatment arms/group

In Part 1 (Safety Run-in), participants enrolled in cohort 1 will receive sabatolimab 400 mg Q4W, and participants enrolled in cohort 2 will receive sabatolimab 800 mg Q4W.

Participants enrolled in Part 2 will receive sabatolimab in monotherapy at the recommended dose for expansion determined in the Safety Run-in (either 400 mg Q4W or 800 mg Q4W) in cohorts 4 and 5 (monotherapy expansion cohort and adolescent cohort respectively), or sabatolimab in combination with azacitidine in cohort 3 (combination cohort).

6.1.4 Guidelines for continuation of treatment

Per protocol, dose modifications, including dose interruptions, for toxicities are permitted and outlined in Section 6.5.

6.1.5 Treatment duration

Study treatment will be administered for up to a maximum of 24 cycles or until a participant experiences hematologic relapse (bone marrow blasts ≥5%; or reappearance of blasts in the blood; or development of extramedullary disease) as defined by ELN 2017 (Döhner et al 2017); or any of the following events, whichever is earlier:

- unacceptable toxicity
- initiation of a treatment cycle is delayed due to toxicities by more than 28 days (measured from the intended start date of the new cycle (i.e. measured from Day 29 of the previous cycle)
- withdrawal of consent
- physician decision
- lost to follow up
- pregnancy
- death

For participants who achieve negative MRD and maintain MRD negativity for 12 consecutive cycles, study treatment (sabatolimab monotherapy or sabatolimab in combination with azacitidine) can be discontinued earlier, at the discretion of the PI.

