6.5.4 Dose modifications

For participants who do not tolerate the protocol-specified dosing schedule, dose interruptions are required to allow participants to continue the study treatment.

Dose modifications for sabatolimab

Dose modifications for sabatolimab will be done according to ASCO guidelines for management of immune-related AEs including hematological AEs. (Brahmer et al 2018)

Additionally, the guidance indicated in Table 6-3 below, provides instructions for infusion reaction, immune-related adverse events not covered by ASCO guidelines and a general guideline for non-hematologic non-immune-related toxicities that are clinically significant per investigator judgement and possibly attributable to the investigational drug. This general guideline will not apply in case of non-hematologic non-immune-related toxicities that are attributable to azacitidine and its complications.

Deviations to dose interruptions, reductions and/or permanent discontinuations outlined in Table 6-3 are not allowed.

Administration of sabatolimab may be delayed due to toxicities. A scheduled dose may be delayed within a cycle by up to 14 days. If a dose cannot be administered within the planned window within the cycle, then the dose should be skipped. Next scheduled dosing may resume once the adverse event has resolved to \leq Grade 1 or baseline per the next planned treatment cycle. Dose reductions for sabatolimab are not allowed.

Overall, for adverse events of potential immune-related etiology (other than GvHD) that do not recover to \leq Grade 1 or baseline and be maintained at a dose of immunosuppression of \leq 10 mg/day prednisone or equivalent (or as indicated in Table 6-3 within 12 weeks after initiation of immunosuppressive therapy), sabatolimab must be permanently discontinued.

For acute and/or chronic GvHD, refer to Table 6-4 for study treatment interruption, reinitiation and/or permanent discontinuation.

Dose interruption at the start of a new treatment cycle (Combination cohort)

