If the study treatment (sabatolimab + azacitidine) is interrupted for toxicities other than GvHD and the start of the subsequent study treatment cycle is delayed for more than 28 consecutive days from the intended start date of cycle (Day 29 of the previous cycle) the participant should be discontinued from study treatment. For permanent discontinuation of study treatment due to acute and/or chronic GvHD, refer to Table 6-4.

Permanent discontinuation of only one component sabatolimab (or azacitidine - Combination cohort)

If **one component only** of the study treatment (azacitidine or sabatolimab) is discontinued for toxicities (other than GvHD), then the treatment may continue with the other component of study treatment alone (sabatolimab alone or azacitidine alone) as long as the participant benefits per investigator's judgement.

These dose changes must be recorded on the appropriate CRF.

^{**}Per investigator judgement

Table 6-4 Criteria for dose interruption, re-initiation and discontinuation of study treatment due to GvHD

	y treatment due to G	T	Diagontino ()				
	Interrupt study treatment [£] (sabatoli mab monotherapy or in combination with azacitidine)	Resume study treatment (sabatolimab monotherapy or in combination with azacitidine)	Discontinue study treatment permanently (sabatolimab monotherapy or in combination with azacitidine)				
Acute GvHD (aGvHD)	New onset grade II requiring systemic therapy New onset grade III Baseline grade I or II worsening to grade III III III III III III III II	 If aGvHD improved to ≤ grade I or to baseline prior to starting study treatment within ≤ 8 weeks of observation from onset or exacerbation of aGvHD The following are allowed at time of resumption of study treatment: Topical, nonabsorbable or inhaled steroids Systemic doses of steroids ≤ 10 mg prednisone or equivalent Tacrolimus with trough levels <5 ng/mL OR CSA with trough levels <200 ng/mL (indicating continuous IST taper) 	 Grade IV aGvHD Recurrence or exacerbation of aGvHD to ≥ grade III after resuming study treatment Steroid-refractory aGvHD No improvement to ≤ grade I or to baseline prior to starting study treatment after 8 weeks of observation from onset or exacerbation of aGvHD 				

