Note: If a treatment cycle is delayed at any time during the study, all study visits and safety and efficacy assessments should continue according to the appropriate number of calendar days measured from Day 1 of the previous cycle, or more often if clinically indicated. In the combination cohort, when treatment is resumed, the first day of azacitidine administration will be considered as D1 of the new treatment cycle and visit schedule will be shifted accordingly. If sabatolimab administration on Day 5 is delayed within a cycle due to toxicities, visit assessments for Day 5 should be shifted accordingly.

On PK collection days the windows and time points are provided in Section 8.5.2.

Participants who discontinue the study treatment for any reason should be scheduled for an end of treatment (EOT) visit within 14 days from the decision to permanently discontinue study treatment, at which time all of the assessments listed for the EOT visit will be performed.

For post-treatment follow-up information, please refer to Section 9.1.1.2.

Table 8-1 Assessment Schedule, Sabatolimab monotherapy cohort

Period	Pre- Screening	Screening		Treatment								Safety Follow-up	Post-Treatment Follow-up	
Cycle				cle 1	-	ele 2	Cycle 3	Cycle 4	Cycle 5	Cycle 6	Cycle 7 (and subsequent cycles up to Cycle 24)			
Days	NA	-28 to -1	D1	D15	D1 ±3	D15	D1 ±3	D1 ±3	D1 ±3	D1 ±3	D1 ±3	EOT	30,90,150 days	Every 12 weeks
Pre-screening Informed Consent	Х													
Informed consent		Х												
IRT Registration	Х	Х	Χ									Х		
Demography		Х												
Inclusion / Exclusion criteria		Х												
AML Disease History [aHSCT and GvHD (acute and chronic) history]		х												
MRD History ²		Х												
Other relevant Medical History /Current medical conditions		х												
Prior medications (including prior antineoplastic therapies, prophylactic DLI), surgery, and medical procedures		х							(continu	ous		X	

Period	Pre- Screening	Screening		Treatment								ЕОТ	Safety Follow-up	Post-Treatment Follow-up
Cycle				le 1	Cycle 2		Cycle 3	Cycle 4	Cycle 5	Cycle 6	Cycle 7 (and subsequent cycles up to Cycle 24)			
Days	NA	-28 to -1	D1	D15	D1 ±3	D15	D1 ±3	D1 ±3	D1 ±3	D1 ±3	D1 ±3	EOT	30,90,150 days	Every 12 weeks
Physical Examination		S	s	S	S	S	S	S	S	S	S	S		
Vital Signs		Х	Х	Х	Х	Х	Х	Х	Х	Х	X	Х		
Body Height		Х												
Body Weight		Х	Х		Х		Х	Х	Х	Х	X	Х		
Performance Status Score ³		Х	Х		Х		Х	Х	х	х	X	Х		

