9.1 Discontinuation and completion

9.1.1 Study treatment discontinuation and study discontinuation

Discontinuation of study treatment will occur when a participant has documented relapse from CR/CRi or until for any of the reasons described below, and can be initiated by either the participant or the investigator.

The investigator must discontinue study treatment for a given participant if, he/she believes that continuation would negatively impact the participant's well-being.

Study treatment must be discontinued under the following circumstances:

- participant/guardian decision
- Pregnancy

- Use of prohibited treatment as per recommendations in the prohibited treatment (Section 6.2.2)
- Any situation in which study participation might result in a safety risk to the participant
- Any adverse events or laboratory abnormalities that in the judgment of the investigator, taking into consideration the participant's overall status, prevents the participant from continuing the study treatment
- Protocol-defined reasons for treatment discontinuation (see Section 6.1.4 and Section 6.1.5)
- Termination of the study by Novartis

If discontinuation of study treatment occurs due to circumstances other that the protocol defined criteria in Section 6.1.4 and Section 6.1.5, the investigator should make a reasonable effort to understand the primary reason for the participant's premature discontinuation of study treatment and record this information.

Participants who discontinue study treatment or who decide they do not wish to participate in the study further should NOT be considered withdrawn from the study UNLESS they withdraw their consent (see 'Withdrawal of Informed Consent' Section 9.1.2). Where possible, they should return for the assessments indicated in the Assessment Schedule. If they fail to return for these assessments for unknown reasons, every effort (e.g. telephone, e-mail, letter) should be made to contact the participant/pre-designated contact as specified in the lost to follow-up section. This contact should preferably be done according to the study visit schedule.

If the participant cannot or is unwilling to attend any visit(s), the site staff should maintain regular telephone contact with the participant, or with a person pre-designated by the participant. This telephone contact should preferably be done according to the study visit schedule.

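### Section 6.1.5 stops treatment after a cycle delay of more than 28 days for toxicity with no GvHD exception, while Table 6-4 allows 8 weeks for GvHD recovery; the cGvHD resume cell also counts from the wrong event

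*Protocol*

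**What the plan says.** Protocol 6.1.5 lists the events that end study treatment. One is that "initiation of a treatment cycle is delayed due to toxicities by more than 28 days", measured from Day 29 of the previous cycle. The bullet names no cohort and makes no exception. Section 9.1.1 then lists, among the circumstances in which treatment must be discontinued, "Protocol-defined reasons for treatment discontinuation (see Section 6.1.4 and Section 6.1.5").

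Table 6-4, in 6.5.4, deals with GvHD. Its columns cover sabatolimab monotherapy and the combination. For acute GvHD, treatment may resume on improvement to grade I or less, or to baseline, "within ≤ 8 weeks of observation from onset or exacerbation of aGvHD". It stops permanently if that improvement has not come after 8 weeks, or on other listed criteria such as grade IV disease.

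Section 6.5.4 repeats the 28-day stop for the combination cohort, and there it applies when study treatment "is interrupted for toxicities other than GvHD and the start of the subsequent study treatment cycle is delayed for more than 28 consecutive days". For sabatolimab in general, 6.5.4 says: "For acute and/or chronic GvHD, refer to Table 6-4 for study treatment interruption, reinitiation and/or permanent discontinuation". It also says "A scheduled dose may be delayed within a cycle by up to 14 days", and "If a dose cannot be administered within the planned window within the cycle, then the dose should be skipped".

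In the chronic GvHD row of Table 6-4, the resume cell also ends with the words "within ≤ 8 weeks of observation from onset or exacerbation of aGvHD", whereas the discontinue cell in that row counts its 8 weeks from cGvHD.

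**The concern.** The protocol treats GvHD as an immune-mediated toxicity (1.2), so a GvHD hold falls within the plain wording of 6.1.5. A participant who recovers late in the 8-week window may then be eligible for re-dosing under Table 6-4 and required to stop under 6.1.5. The sponsor evidently saw the need for an exemption, since it is written into 6.5.4, but it sits under a heading limited to the combination cohort.

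What is at stake is whether a participant is re-exposed to sabatolimab after GvHD, which 1.2 names as the principal safety concern in this setting. That decision should not depend on which section a site reads.

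The slip in the chronic GvHD row does not depend on how cycles are counted. Read literally, a participant with chronic but no acute GvHD has no starting point for the resumption clock.

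**Working it through.** The plan gives no figure to reproduce; the check compares two clocks.

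**Inputs.** Count days from Day 1 of the cycle in which GvHD begins.
- Intended next cycle start: Day 29 (28-day cycles).
- 6.1.5: a start up to 28 days late is allowed, so the last permitted start is Day 29 + 28 = Day 57.
- Table 6-4: 8 weeks = 56 days, so for onset on Day k the last qualifying recovery is Day k + 56.
- Assumption: infusion on the day of recovery, with the Table 6-4 conditions on steroid dose and tacrolimus or CSA troughs met.

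**If the held dose delays the cycle.** Days late at the Table 6-4 limit = (k + 56) − 29. Days past the 6.1.5 limit = (k + 56) − 57 = k − 1.

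| Onset day k | Last Table 6-4 day | Days late against Day 29 | Days past Day 57 |
|---|---|---|---|
| 1 | 57 | 28 | 0 |
| 2 | 58 | 29 | 1 |
| 15 | 71 | 42 | 14 |
| 28 | 84 | 55 | 27 |
| 29 | 85 | 56 | 28 |

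The first row assumes the Day 1 dose was given. The last is GvHD found at the next visit before dosing.

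Example: onset Day 15, recovery Day 65. From onset: 65 − 15 = 50 days, within 56, so treatment may resume. Against the intended start: 65 − 29 = 36 days, over 28, so treatment must stop.

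**If the held dose is skipped and cycles run on.** Same example: the Day 29 dose is skipped, and Cycle 3 Day 1 is Day 57. An infusion on Day 65 is 65 − 57 = 8 days late, inside the 14-day limit (57 + 14 = Day 71). The 28-day stop is not triggered and there is no conflict.

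**Which reading applies to monotherapy.** The text points both ways.
- For skipping: the 6.5.4 sentences quoted above. Section 8 also resets Day 1 on resumption for one cohort only: "In the combination cohort, when treatment is resumed, the first day of azacitidine administration will be considered as D1 of the new treatment cycle".
- For delaying: the primary safety estimand (2.1), which concerns monotherapy, lists a delayed Cycle 3 start as an intercurrent event. Section 8 provides for delayed cycles at any time without naming a cohort. SAP 5.1 dates a monotherapy cycle from the sabatolimab infusion. The skip paragraph also sets its restart condition by toxicity grade, while 6.5.3 excludes GvHD from CTCAE grading.

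**The case against.** The strongest reply is that the intent is clear enough. The 9.1.1 bullet cites 6.1.4 as well as 6.1.5, and 6.1.4 sends dose interruptions to Section 6.5. Sections 6.2.2, 6.5.3 and 6.5.4 all refer GvHD to Table 6-4, whose column headings include monotherapy. On the usual principle that the specific rule governs the general one, the table prevails. In monotherapy the skip rule may also prevent the 28-day stop from ever being reached. Most of this stands: Table 6-4 was probably meant to govern, and the monotherapy conflict is conditional. But no sentence says the table overrides 6.1.5, and the one express exemption is confined to the combination cohort.

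A second reply is that exempting GvHD alone could imply that the 28-day stop binds other toxicities that have longer limits elsewhere (56 days in Table 6-3; 12 weeks for immune-related events in 6.5.4). The 6.1.5 bullet already covers all toxicities as written, so the edit leaves that question where it is.

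A reader might go further and infer three things the documents do not support.
- *That a typical share of the 8-week window is in dispute.* An average needs a distribution of GvHD onset days, and neither document gives one. Only the onset-by-onset figures above can be stated.
- *That DLT evaluability in the run-in is compromised.* Section 9.1.1.3 allows new participants to be enrolled when too few are evaluable, Section 3 plans about 8 to obtain 6 and about 12 to obtain 9, and 2.1 and SAP 2.2 state how a delayed or missing Cycle 3 is handled.
- *That the efficacy conclusion is at risk.* The primary efficacy estimand (2.1) uses treatment policy for stopping for reasons other than relapse or death, GvHD included.

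**Conclusion.** The concern holds as a minor inconsistency between dosing rules. A mandatory general stop with no GvHD exception sits beside a GvHD-specific table allowing up to 8 weeks for recovery, and the only written exemption covers the combination cohort.

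If a held monotherapy dose delays the cycle, the rules disagree on the last k − 1 days of the window: none for onset on Day 1, 14 days for Day 15, and 28 days for GvHD found before dosing on Day 29. If the dose is skipped, they do not collide in the worked example. It would overstate the matter to say that monotherapy participants are always caught between the rules.

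The chronic GvHD cell is a plain drafting error under either reading. The consequence is possible inconsistency between sites in re-exposure after GvHD, with little effect on primary efficacy. The documents do not show whether any participant was affected. The SAP reports that recruitment has stopped and the program has ended, which further limits the practical reach.

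**What to change.** Make two edits to the protocol.
1. In the 6.1.5 bullet, limit the 28-day stop to *toxicities other than GvHD (for GvHD see Table 6-4)*. This carries the sponsor's own 6.5.4 exemption to all cohorts, and it removes the GvHD conflict whether a held dose is skipped or delays the cycle.
2. In the cGvHD resume cell of Table 6-4, count the 8 weeks from onset or exacerbation of *cGvHD*, to agree with the discontinue cell in the same row.

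The cost is two short wording changes, with no new data, assessments or analyses. No change to Table 6-3 or to the limits for immune-related events is proposed.

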6.1.5.1 Treatment beyond disease progression

Treatment beyond hematologic relapse is not permitted.

6.2 Other treatment(s)

6.2.1 Concomitant therapy

In general, the use of any concomitant medication/therapy deemed necessary for the care of the participant (e.g., such as anti-emetics, anti-diarrheal) is permitted (see Section 6.2.1.1), except when specifically prohibited (see Section 6.2.2). The participant must be told to notify the investigational site about any new medications he/she takes after the start of the study drug.

Participants should not receive pre-medication to prevent infusion reaction before the first infusion of sabatolimab. If a participant experiences an infusion reaction, he/she may receive pre-medication on subsequent dosing days. The pre-medication should be chosen per institutional standard of care, at the discretion of the treating physician. If a participant experiences a Grade 3 infusion reaction (which does not resolve within 72 hrs) or Grade 4 infusion reaction, the investigational drug (sabatolimab) should be discontinued (see Table 6-3).

Acute allergic reactions should be treated as needed per institutional standard of care. In the event of anaphylactic/anaphylactoid reactions, this includes any therapy necessary to restore normal cardiopulmonary status. If a participant experiences a Grade 3 anaphylactic/anaphylactoid reaction, the participant will be discontinued from the study treatment.

Sabatolimab should be administered in a facility equipped for cardiopulmonary resuscitation. Appropriate resuscitation equipment should be available at the bedside and a physician readily available.

Participants should receive appropriate prophylaxis (e.g. antiemetics) for azacitidine as per local practice.

For participants enrolled all medications, procedures, and significant non-drug therapies/procedures (including physical therapy) taken within the 28 days of screening until 150 days after the last dose of sabatolimab or 30 days after the last dose of azacitidine administered, whichever is later, or until start of a new antineoplastic therapy must be recorded in the appropriate Case Report Forms. Concomitant medication administered to treat AE/SAEs suspected to be related to study treatment will continue to be collected up to the end of the safety follow-up period.

The approved drug labels for azacitidine should be consulted for guidance on concomitant therapies.

Each concomitant drug must be individually assessed against all exclusion criteria/prohibited medication. If in doubt, the investigator should contact the Novartis medical monitor before enrolling a participant or allowing a new medication to be started. If the participant is already enrolled, contact Novartis medical monitor to determine if the participant should continue study treatment.

6.2.1.1 Permitted concomitant therapy requiring caution and/or action

Anticoagulation therapy is permitted if the participants are already at stable dose of warfarin or stable doses of low molecular weight heparin (LMWH) for > 2 weeks at time of first dose and International Normalized Ratio (INR) should be monitored as clinically indicated per investigator's discretion. Participants who develop a new requirement for anticoagulant

therapy during the conduct of the study may remain on study after documented discussion with the Novartis medical monitor. However, ongoing anticoagulant therapy should be temporarily discontinued to allow bone marrow sampling according to the institutional guidelines.

Anti-hypertensive therapy is allowed as concomitant medications; however, because transient hypotension has occurred during infusions of monoclonal antibodies, consideration should be given to withholding anti-hypertensive medications for 12 hours prior to infusion with sabatolimab.

6.2.2 Prohibited medication

During the course of study treatment, participants must not receive additional investigational drugs or devices, chemotherapy, DLI, other cellular therapies or any other therapies that may be active against cancer or modulate the immune response. Post treatment efficacy follow-up period will end, once a participant develops a hematologic relapse, or start of new therapy for AML.

Additionally, the use of systemic corticosteroids and/or immunosuppressive medications is not allowed while on study treatment unless given for the management of infusion-related reaction, treatment-emergent immune-related adverse events (irAEs), aGvHD and/or cGvHD.

Systemic corticosteroids required for control of infusion-related reactions or irAEs must be tapered and be at non-immunosuppressive doses (≤ 10 mg/day of prednisone or equivalent corticosteroid dose) before the next study administration. If more than 10 mg/day prednisone is used, sabatolimab should be interrupted until the participant receives 10 mg/day or less of prednisone. Topical, inhaled, non-absorbable, nasal and ophthalmic steroids are allowed.

For aGvHD and/or cGvHD, refer to Table 6-4.

The use of systemic steroids and/or other immunosuppressive drugs may be administered for prophylaxis against imaging contrast dye allergy (providing this is ≤ 10 mg/day prednisone or equivalent corticosteroid dose), or replacement-dose steroids in the setting of adrenal insufficiency, or for the management of transient exacerbation of other underlying diseases such as chronic obstructive pulmonary disease requiring treatment for ≤ 3 weeks.

The use of live vaccines is not allowed through the duration of the study treatment and 150 days after the last dose of sabatolimab. Inactivated vaccines, subunit, recombinant, polysaccharide and conjugate vaccines and toxoid vaccines are allowed.

In addition, prohibited medication related to azacitidine will apply according to local/global label.

